**Table 20 Schedule of Activities – Screening Period – Part B, Hot-only Dose Escalation (if Applicable)**

Assessments/procedures a	General Screening D-28 to ~D-15	[  In]-FPI-2107 Imaging Screening Period					Details in Section/Appendix	
		[  In]-FPI-2107 D1		24 h (±6 h) Post-inj. of [  In]- FPI-2107	48 h (±6 h) Post-inj. of [  In]- FPI-2107	72-96 h (±6 h) Post-inj. of [  In]- FPI-2107		
		Pre-inj.	Inj.					
Informed consent, demographics	X						A 3	
Eligibility criteria	X						5.1 & 5.2	
Medical history	X						5.1 & 5.2	
Concomitant medications	X	X	X	X	X	X	6.6	
AE monitoring				Continuous monitoring				8.5
Haematology (whole blood)	X	X		X			8.4.4	
Coagulation tests	X	X					8.4.4	
Clinical chemistry (serum or plasma)	X	X		X			8.4.4	
Thyroid panel	X						8.4.4	
Urinalysis	X						8.4.4	
Pregnancy test (blood or urine in accordance with institutional practice)	X	X					8.4.4	
Complete physical examination	X						8.4.1	
Symptom-directed physical examination		X	X				8.4.1	

Assessments/procedures a	General Screening D-28 to ~D-15	[  In]-FPI-2107 Imaging Screening Period						Details in Section/Appendix
		[  In]-FPI-2107 D1		24 h (±6 h) Post-inj. of [  In]- FPI-2107	48 h (±6 h) Post-inj. of [  In]- FPI-2107	72-96 h (±6 h) Post-inj. of [  In]- FPI-2107	28-Day Safety Visit b	
		Pre-inj.	Inj.					
ECOG Performance Status	X						X	8.4.5
Height	X							8.4.1
Weight	X	X						8.4.1
Vital signs	X	X c	X c	X	X		X	8.4.2
Ophthalmologic examination	X						X	8.4.6.2
ECG (12-lead)	Table 28							8.4.3
[  In]-FPI-2107 administration			X					6.1
Whole body planar scintigraphy d				X				8.3.2
SPECT/CT imaging e,f				X				8.3.1
CT or MRI for RECIST 1.1 Response Assessments g	X							8.2
Blood for TCR analysis	Table 28							8.8.1.1
Blood for RNA analysis	Table 28							8.8.1.1
Plasma for ctDNA analysis	Table 28							8.8.1.2
Serum for tumour marker measurement (e.g., CA-19-9, CEA, etc.)	X							8.8.1.3
PK samples	Table 28							8.7.1
ADA samples	Table 28							8.7.2
Archival sample (within 12	X							8.8.1.4

Assessments/procedures a	General Screening D-28 to ~D-15	[  In]-FPI-2107 Imaging Screening Period					Details in Section/Appendix
		[  In]-FPI-2107 D1		24 h (±6 h) Post-inj. of [  In]- FPI-2107	48 h (±6 h) Post-inj. of [  In]- FPI-2107	72-96 h (±6 h) Post-inj. of [  In]- FPI-2107	
		Pre-inj.	Inj.				
months) or fresh biopsy							

ADA, anti-drug antibody; AE, adverse event; CA-19-9, carbohydrate antigen-19-9; CEA, carcinoembryonic antigen; CT, computed tomography; ctDNA, circulating tumour DNA; D, day; ECG, electrocardiogram; ECOG, Eastern Cooperative Oncology Group; inj., injection; MRI, magnetic resonance imaging; PK, pharmacokinetics; RECIST, Response Evaluation Criteria in Solid Tumours; RNA, ribonucleic acid; SPECT, single-photon emission computed tomography; TCR, T-cell receptor.

- a If clinically indicated, any procedure or assessment may be done as an unscheduled visit.
- b Participants who only received [In]-FPI-2107 should have a Day 28 (± 3 days) safety visit as their last study visit (safety laboratory tests, physical examination, vital signs, AE assessment, and concomitant medications).
- c Vital signs to be collected at pre-injection (± 5 minutes), end of injection (± 5 minutes), and 4 hours (± 30 minutes) post injection on day of [In]-FPI-2107.
- d Planar imaging will be acquired at 4 time points for dosimetry calculation after [In]-FPI-2107 administration. Please refer to the Site Imaging Manual for timing of the scans, as precise timing may be revised over the course of the study.
- e SPECT/CT should include relevant body area(s) with known tumour involvement as determined by the Investigator and/or nuclear medicine physician, as well as bone marrow, liver, kidney, and lung.
- f Only two SPECT/CT images need to be obtained between 24 and 96 hours post [In]-FPI-2107 injection; please refer to the Site Imaging Manual for timing of the scans, as precise timing may be revised over the course of the study.
- g The same assessment modality (CT or MRI as appropriate) should be used at baseline and throughout the study.

### 8.1.4 Treatment Period - Part A (Dose Exploration with Unlabelled bsAb) - Cycle 1

**Table 21 Schedule of Assessments - Treatment Period - Part A (Dose Exploration with Unlabelled bsAb) - Cycle 1**

Assessments/procedures a	[  Ac]-FPI-2068 Cycle 1 b								Details in Section/Appendix								
	Day 1		[  Ac]-FPI-2068	Day 8 (± 1 D)	Day 15 (± 2 D)	Day 22 (± 2 D)	Day 29 (± 3 D)	Day 36 (± 3 D)									
	FPI-2053																
	Pre-inj.	Inj.															
Eligibility criteria c	X								5.1 & 5.2								
Concomitant medications and procedures	X			X	X	X	X	X	6.6								
AE monitoring d	Continuous monitoring								8.5								
Haematology (whole blood)	X			X	X	X	X	X	8.4.4								
Coagulation tests	As clinically indicated								8.4.4								
Clinical chemistry (serum or plasma)	X			X	X	X	X	X	8.4.4								
Thyroid panel	As clinically indicated								8.4.4								
Urinalysis	X					X			8.4.4								
Pregnancy test (blood or urine, in accordance with institutional practice)	X								8.4.4								
Complete physical examination	X								8.4.1								
Symptom-directed physical examination		X	X	X	X	X	X	X	8.4.1								
ECOG Performance Status	X								8.4.5								
Weight	X								8.4.1								
Vital signs	X	X	X	X	X	X	X	X	8.4.2								
Ophthalmologic examination	As clinically indicated								8.4.6.2								
ECG (12-lead)	Table 26								8.4.3								
FPI-2053 administration		X							6.1								

Assessments/procedures a	[  Ac]-FPI-2068 Cycle 1 b							Details in Section/Appendix	
	Day 1		[  Ac]-FPI-2068	Day 8 (± 1 D)	Day 15 (± 2 D)	Day 22 (± 2 D)	Day 29 (± 3 D)		
	FPI-2053	Pre-inj.							
	Inj.								
[  Ac]-FPI-2068 administration			X					6.1	
CT or MRI for RECIST 1.1 Response Assessments c	Every 8 weeks (± 1 week) after first [  Ac]-FPI-2068 dose							8.2	
Blood for TCR analysis	Table 26							8.8.1.1	
Blood for RNA analysis	Table 26							8.8.1.1	
Plasma for ctDNA analysis	Table 26							8.8.1.2	
Tumour biopsy (if applicable)				Day 8 to Day 11 f				8.8.2.1	
PK samples	Table 26							8.7.1	
ADA samples	Table 26							8.7.2	

ADA, anti-drug antibody; AE, adverse event; bsAb, bispecific monovalent antibody; CT, computed tomography; ctDNA, circulating tumour DNA; D, day; ECG, electrocardiogram; ECOG, Eastern Cooperative Oncology Group; FDG, fluorodeoxyglucose; inj., injection; MRI, magnetic resonance imaging; PET, positron emission tomography; PK, pharmacokinetics; RECIST, Response Evaluation Criteria in Solid Tumours; RNA, ribonucleic acid; TCR, T-cell receptor; TEAE, treatment-emergent adverse event.

a If clinically indicated, any procedure or assessment may be done as an unscheduled visit.

b Each cycle must be at least 56 days duration.

c Obtain within 48 hours prior to the injection and confirm that all tests are within the eligibility requirements.

d AEs reported after [In]-FPI-2107 administration will be reported as TEAEs. All TEAEs related to [In]-FPI-2107 should be resolved to < Grade 1 or to baseline within 14-days post-[In]-FPI-2107 administration and prior to [Ac]-FPI-2068 administration.

e A consistent modality of scanning (CT, MRI) should be used for the participant throughout the course of the study. Participants who experience a PR should have their response confirmed 4-6 weeks following documentation of the initial response. CT scan or MRI of chest, abdomen, and pelvis (and other organs if medically indicated) can be obtained for those with non-avid FDG-PET/CT scan. Tumour assessment scans are only required at 2, 4, 6 months (±1 week) and then every 3 months (±2 weeks) until progression or start of new systemic anti-cancer treatment.

f If a tumour sample can be safely obtained, every effort should be made to collect a core biopsy between Day 8 and Day 11 in Cycle 1 or Cycle 2 of the Treatment Period.

### 8.1.5 Treatment Period - Part B (Hot Dose Escalation with Unlabelled bsAb) – Cycle 1

**Table 22 Schedule of Assessments - Treatment Period - Part B (Hot Dose Escalation with Unlabelled bsAb) – Cycle 1**

Assessments/procedures a	[  Ac]-FPI-2068 Cycle 1 b							Details in Section/Appendix								
	Day 1		[  Ac]-FPI-2068	Day 8 (± 1 D)	Day 15 (± 2 D)	Day 22 (± 2 D)	Day 29 (± 3 D)	Day 36 (± 3 D)								
	FPI-2053															
	Pre-inj.	Inj.														
Eligibility criteria c	X								5.1 & 5.2							
Concomitant medications and procedures	X			X	X	X	X	X	6.6							
AE monitoring d	Continuous monitoring								8.5							
Haematology (whole blood)	X			X	X	X	X	X	8.4.4							
Coagulation tests	As clinically indicated								8.4.4							
Clinical chemistry (serum or plasma)	X			X	X	X	X	X	8.4.4							
Thyroid panel	As clinically indicated								8.4.4							
Urinalysis	X					X			8.4.4							
Pregnancy test (blood or urine, in accordance with institutional practice)	X								8.4.4							
Complete physical examination	X								8.4.1							
Symptom-directed physical examination		X	X	X	X	X	X	X	8.4.1							
ECOG Performance Status	X								8.4.5							
Weight	X								8.4.1							
Vital signs	X	X	X	X	X	X	X	X	8.4.2							
Ophthalmologic examination	As clinically indicated								8.4.6.2							
ECG (12-lead)	Table 27								8.4.3							
FPI-2053 administration		X							6.1							

Assessments/procedures a	[  Ac]-FPI-2068 Cycle 1 b							Details in Section/Appendix								
	Day 1		[  Ac]-FPI-2068	Day 8 (± 1 D)	Day 15 (± 2 D)	Day 22 (± 2 D)	Day 29 (± 3 D)	Day 36 (± 3 D)								
	FPI-2053															
	Pre-inj.	Inj.														
[  Ac]-FPI-2068 administration			X						6.1							
CT or MRI for RECIST 1.1 Response Assessments c	Every 8 weeks (± 1 week) after first [  Ac]-FPI-2068 dose								8.2							
Blood for TCR analysis	Table 27								8.8.1.1							
Blood for RNA analysis	Table 27								8.8.1.1							
Plasma for ctDNA analysis	Table 27								8.8.1.2							
Tumour biopsy (if applicable) f				Day 8 to Day 11					8.8.2.1							
PK samples	Table 27								8.7.1							
ADA samples	Table 27								8.7.2							

ADA, anti-drug antibody; AE, adverse event; bsAb, bispecific monovalent antibody; CT, computed tomography; ctDNA, circulating tumour DNA; D, day; ECG, electrocardiogram; ECOG, Eastern Cooperative Oncology Group; FDG, fluorodeoxyglucose; inj., injection; MRI, magnetic resonance imaging; PK, pharmacokinetics; PET, positron emission tomography; RECIST, Response Evaluation Criteria in Solid Tumours; RNA, ribonucleic acid; TCR, T-cell receptor; TEAE, treatment-emergent adverse event.

a If clinically indicated, any procedure or assessment may be done as an unscheduled visit.

b Each cycle must be at least 56 days duration.

c Obtain within 48 hours prior to the injection and confirm that all tests are within the eligibility requirements.

d All TEAEs related to [In]-FPI-2107 should be resolved to < Grade 1 or to baseline prior to [Ac]-FPI-2068 administration.

e A consistent modality of scanning (CT, MRI) should be used for the participant throughout the course of the study. Participants who experience a PR should have their response confirmed 4-6 weeks following documentation of the initial response. CT scan or MRI of chest, abdomen, and pelvis (and other organs if medically indicated) can be obtained for those with non-avid FDG-PET/CT scan. Tumour assessment scans are only required at 2, 4, 6 months (±1 week) and then every 3 months (±2 weeks) until progression or start of new systemic anti-cancer treatment.

f If a tumour sample can be safely obtained, every effort should be made to collect a core biopsy between Day 8 and Day 11 in Cycle 1 or Cycle 2 of the Treatment Period.

**8.1.6 Treatment Period - Part B – Hot-only Dose Escalation (in the Event that Results from Part A Indicate that Dose Escalation Without Pre-administration of FPI-2053 is Recommended)**

**Table 23 Schedule of Assessments - Treatment Period - Part B – Hot-only Dose Escalation (if Applicable)**

Assessments/procedures a	[  Ac]-FPI-2068 Cycle 1 b						[  Ac]-FPI-2068 Cycle 2 and beyond b			Details in Section/Appendix	
	Day 1		Day 8 (± 1 D)	Day 15 (± 2 D)	Day 22 (± 2 D)	Day 29 (± 3 D)	Day 36 (± 3 D)	Day 1 (± 3D)			
	Pre-inj.	Post-inj.						Pre-inj.	Post-inj.		
Eligibility/retreatment criteria c (see Table 15)	X							X			
Concomitant medications and procedures	X		X	X	X	X	X	X		X	
AE monitoring d	X		Continuous monitoring							8.5	
Haematology (whole blood)	X		X	X	X	X	X	X		X	
Coagulation tests			As clinically indicated							8.4.4	
Clinical chemistry (serum or plasma)	X		X	X	X	X	X	X		X	
Thyroid panel								X			
Urinalysis	X				X			X			
Pregnancy test (blood or urine, in accordance with institutional practice)	X							X			
Complete physical examination	X									8.4.1	
Symptom-directed physical examination		X	X	X	X	X	X	X	X	8.4.1	
ECOG Performance Status	X							X		8.4.5	
Weight	X							X		8.4.1	

Assessments/procedures a	[  Ac]-FPI-2068 Cycle 1 b							[  Ac]-FPI-2068 Cycle 2 and beyond b			Details in Section/Appendix	
	Day 1		Day 8 (± 1 D)	Day 15 (± 2 D)	Day 22 (± 2 D)	Day 29 (± 3 D)	Day 36 (± 3 D)	Day 1 (± 3D)		Day 15 and Day 29 (± 3 D)		
	Pre-inj.	Post-inj.		Pre-inj.	Post-inj.	Pre-inj.	Post-inj.					
Vital signs	X	X	X	X	X	X	X	X	X	X	8.4.2	
Ophthalmologic examination	As clinically indicated										8.4.6.2	
ECG (12-lead)	Table 28										8.4.3	
[  Ac]-FPI-2068 administration		X							X		6.1	
CT or MRI for RECIST 1.1 Response Assessments c								Every 8 weeks, or as clinically indicated			8.2	
Serum for tumour marker measurement (e.g., CA-19-9, CEA, etc.)								X f			8.8.1.3	
Blood for TCR analysis	Table 28										8.8.1.1	
Blood for RNA analysis	Table 28										8.8.1.1	
Plasma for ctDNA analysis	Table 28										8.8.1.2	
Tumour biopsy (if applicable)			Day 8 to Day 11 g								8.8.2.1	
PK samples	Table 28										8.7.1	
ADA samples	Table 28										8.7.2	

ADA, anti-drug antibody; AE, adverse event; CA-19-9, carbohydrate antigen-19-9; CEA, carcinoembryonic antigen; CT, computed tomography; ctDNA, circulating tumour DNA; D, day; ECG, electrocardiogram; ECOG, Eastern Cooperative Oncology Group; inj., injection; MRI, magnetic resonance imaging; PK, pharmacokinetics; PR, partial response; RECIST, Response Evaluation Criteria in Solid Tumours; RNA, ribonucleic acid; TCR, T-cell receptor; TEAE, treatment-emergent adverse event.

a If clinically indicated, any procedure or assessment may be done as an unscheduled visit.

b Each cycle must be at least 56 days duration.

c Obtain within 48 hours prior to the injection and confirm that all tests are within the eligibility requirements.

d All TEAEs related to [In]-FPI-2107 should be resolved to < Grade 1 or to baseline prior to [Ac]-FPI-2068 administration.

- e A consistent modality of scanning (CT, MRI) should be used for the participant throughout the course of the study. Participants who experience a PR should have their response confirmed 4-6 weeks following documentation of the initial response. CT scan or MRI of chest, abdomen, and pelvis (and other organs if medically indicated) can be obtained for those with non-avid FDG-PET/CT scan. Tumour assessment scans are only required at 2, 4, 6 months ( $\pm$ 1 week) and then every 3 months ( $\pm$ 2 weeks) until progression or start of new systemic anti-cancer treatment.
- f Tumour markers to be obtained, if applicable, at approximately the same time as radiologic tumour assessments ( $\pm$  7 days).
- g If a tumour sample can be safely obtained, every effort should be made to collect a core biopsy between Day 8 and Day 11 in Cycle 1 or Cycle 2 of the Treatment Period.

### 8.1.7 Treatment Period – Part A and Part B ≥ Cycle 2

**Table 24** Schedule of Assessments - Treatment Period – Part A and Part B ≥ Cycle 2

Assessments/procedures a	Cycle 2 and beyond – Treatment Period b					Details in Section/Appendix					
	Day 1		[  Ac]-FPI-2068	Day 15 (± 2 D)	Day 29 (± 3 D)						
	FPI-2053										
	Pre-Inj.	Inj.									
Retreatment criteria (see Table 15 ) c	X					6.7					
Concomitant medications and procedures			Continuous monitoring			6.6					
AE monitoring			Continuous monitoring			8.5					
Haematology (whole blood)	X			X	X	8.4.4					
Coagulation tests			As clinically indicated			8.4.4					
Clinical chemistry (serum or plasma)	X			X	X	8.4.4					
Thyroid panel	X					8.4.4					
Urinalysis	X				X	8.4.4					
Pregnancy test (blood or urine, in accordance with institutional practice)	X					8.4.4					
Symptom directed physical examination d	X			X	X	8.4.1					
ECOG Performance Status	X				X	8.4.5					
Weight	X				X	8.4.1					
Vital signs d	X		X	X	X	8.4.2					
Ophthalmologic examination			As clinically indicated			8.4.6.2					
ECG (12-lead)			Table 26 (Part A), Table 27 (Part B)			8.4.3					
FPI-2053 administration		X				6.1					
[  Ac]-FPI-2068 administration e, f			X			6.1					
CT or MRI for RECIST 1.1 Response Assessments g	Every 8 weeks (± 1 week) after first [  Ac]-FPI-2068 dose					8.2					

Assessments/procedures a	Cycle 2 and beyond – Treatment Period b					Details in Section/Appendix					
	Day 1		[  Ac]-FPI-2068	Day 15 (± 2 D)	Day 29 (± 3 D)						
	FPI-2053										
	Pre-Inj.	Inj.									
Serum for tumour marker measurement (e.g., CA-19-9, CEA, etc.) h	X				X	8.8.1.3					
Blood for TCR analysis	Table 26 (Part A), Table 27 (Part B)					8.8.1.1					
Blood for RNA analysis	Table 26 (Part A), Table 27 (Part B)					8.8.1.1					
Plasma for ctDNA analysis	Table 26 (Part A), Table 27 (Part B)					8.8.1.2					
Tumour biopsy (if applicable) i				Day 8 to Day 11		8.8.2.1					
PK samples	Table 26 (Part A), Table 27 (Part B)					8.7.1					
ADA samples	Table 26 (Part A), Table 27 (Part B)					8.7.2					

ADA, anti-drug antibody; AE, adverse event; CA-19-9, carbohydrate antigen-19-9; CEA, carcinoembryonic antigen; CT, computed tomography; ctDNA, circulating tumour DNA; D, day; ECG, electrocardiogram; ECOG, Eastern Cooperative Oncology Group; inj., injection; MRI, magnetic resonance imaging; PK, pharmacokinetics; RECIST, Response Evaluation Criteria in Solid Tumours; RNA, ribonucleic acid; TCR, T-cell receptor; TEAE, treatment-emergent adverse event.

a If clinically indicated, any procedure or assessment may be done as an unscheduled visit.

b [Ac]-FPI-2068 is administered as a multi-dose regimen. Cycles 2 and 3 to be administered over 56 + 28 days during the Treatment Period.

c Obtain within 48 hours prior to the injection and confirm that all tests are within the eligibility requirements.

d Vital signs to be collected prior to PK sample draw, at pre-injection, end of injection, and 4 hours post injection on day of [Ac]-FPI-2068 prior to FPI-2053 administration.

e All TEAEs related to [Ac]-FPI-2068 should be resolved to < Grade 1 or to baseline prior to [Ac]-FPI-2068 administration.

f To occur within approximately 2 hours after FPI-2053 administration.

g A consistent modality of scanning (CT, MRI) should be used for the participant throughout the course of the study. Participants who experience a PR should have their response confirmed 4-6 weeks following documentation of the initial response. CT scan or MRI of chest, abdomen, and pelvis (and other organs if medically indicated) can be obtained for those with non-avid FDG-PET/CT scan. Tumour assessment scans are only required at 2, 4, 6 months (±1 week) and then every 3 months (±2 weeks) until progression or start of new systemic anti-cancer treatment.

h Tumour markers to be obtained, if applicable, at approximately the same time as radiologic tumour assessments (± 7 days).

i If a tumour sample can be safely obtained, every effort should be made to collect a core biopsy between Day 8 and Day 11 in Cycle 1 or Cycle 2 of the treatment period. A core biopsy does not need to be collected in Cycle 2 if one has already been collected in Cycle 1.

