Prior to the administration of [Ac]-FPI-2068, all AEs related to [In]-FPI-2107 or FPI-2053 should be resolved to Grade 1 or baseline. A delay of 28 days is acceptable from the time of the last [In]-FPI-2107 ( $\pm$  FPI-2053) administration to the administration of [Ac]-FPI-2068 if an AE related to [In]-FPI-2107 or FPI-2053 requires longer time for resolution. In circumstances (e.g., intercurrent illness, etc.) where a delay of [Ac]-FPI-2068 administration may be necessary, the Sponsor and/or Medical Monitor must be consulted to discuss whether the participant can receive [Ac]-FPI-2068. In this scenario, Sponsor and/or Medical Monitor agreement is required prior to [Ac]-FPI-2068 administration. Laboratory results confirming bone marrow and organ function, within retreatment criteria requirements must be documented within 48 hours prior to each cycle of [Ac]-FPI-2068 administration.

Refer to Sections 8.1.4 through 8.1.7 for the assessment details and timepoints performed, and for the biospecimens and information collected during the Treatment Period.

4. *End of Treatment and 28- or 42-Day (+ 14 days) Safety Follow-Up Period:* Participants who do not receive any [Ac]-FPI-2068 (i.e., those who do not enter the Treatment Period) will have a Day 28 ( $\pm$  3 days) safety visit as their last study visit. Participants who receive treatment with [Ac]-FPI-2068 will have a safety visit on Day 42 (+ 14 days) before entering the Extended Safety Follow-up Period.
5. *Extended Safety Follow-up Period:* Because cumulative radiation exposure may be associated with an increased risk of delayed onset of radiation-induced toxicity, participants will undergo additional safety assessments at 3-month intervals. The Extended Safety Follow-up Period will begin 3 months following the last dose of

[Ac]-FPI-2068, and will continue every 3 months for 2 years, then every 6 months for an additional 3 years up to 5 years, or until the participant withdraws from the study (see Section 7.2). Refer to Section 8.1.8 for the assessment details and timepoints performed, and for the biospecimens and information collected during the Extended Safety Follow-up Period.

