**Table 15      Toxicity Management Guidelines and Retreatment Criteria**

Event	Characteristic	Grade	Management recommendation
Anaemia, leucopenia, or neutropenia	Haemoglobin $\leq$ 9g/dL WBC $< 3 \times 10^9/L$ ANC $< 1.5 \times 10^9/L$	$\geq 2$	Hold [  Ac]-FPI-2068 (with or without FPI-2053) until improvement to Grade 1 or baseline. Dose may be held for up to 4 weeks beyond the next planned dose per CSP (i.e., beyond 56 days). Manage as deemed appropriate by Investigator. Use of growth factors is permitted but should be discontinued once the AE resolves to Grade 1 or baseline. Transfusions may be given as clinically indicated for anaemia.
Thrombocytopenia	Platelets: $> 50 \times 10^9/L$ and $< 75 \times 10^9/L$	2	Hold [  Ac]-FPI-2068 (with or without FPI-2053) until improvement to Grade 1 or baseline, retreat at the same dose level. Manage as deemed appropriate by Investigator. Transfusions may be given as clinically indicated for thrombocytopenia.
	Platelets: $< 50 \times 10^9/L$	3 and 4	Hold [  Ac]-FPI-2068 (with or without FPI-2053) until improvement to Grade 1 or baseline, reduce by one dose level. Manage as deemed appropriate by Investigator. Transfusions may be given as clinically indicated for thrombocytopenia.
Increased serum creatinine	CrCl 30-59 mL/min/1.73 m 	2	Hold [  Ac]-FPI-2068 (with or without FPI-2053) until improvement to Grade 1 or baseline. If resolved in $\leq 7$ days, then maintain dose level for the next cycle. If resolved in $> 7$ days, then reduce by one dose level for the next cycle. Manage as deemed appropriate by Investigator.
	CrCl 15-29 mL/min/1.73 m 	3	Treatment should be permanently discontinued.

Event	Characteristic	Grade	Management recommendation
	CrCl < 15-29 mL/min/1.73 m  ; dialysis or renal transplant indicated	4	Treatment should be permanently discontinued.
Increased AST or ALT	> 5.0 - 20 x ULN if baseline was normal; > 5.0 baseline if baseline was abnormal	3	Hold [  Ac]-FPI-2068 (with or without FPI-2053) until improvement to Grade 1 or baseline or ≤ Grade 2 if liver metastases are present. If resolved in ≤ 7 days, then maintain dose level for the next cycle. If resolved in > 7 days, then reduce by one dose level for the next cycle.
	> 20.0 × ULN if baseline was normal; > 20.0 × baseline if baseline was abnormal	4	Treatment should be permanently discontinued.

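### The schedule footnotes, Table 15 and Section 4.1.4 set conflicting conditions for re-dosing with [225Ac]-FPI-2068

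*Protocol*

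**What the plan says.** Conditions for giving a dose of [225Ac]-FPI-2068 appear in four places in the protocol.

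- **Section 6.7.3 and Table 15.** Repeat dosing depends on the Table 15 retreatment criteria. After a hold, Table 15 generally allows dosing once the event is at Grade 1 or baseline. For Grade 2 thrombocytopenia the instruction is to hold "until improvement to Grade 1 or baseline, retreat at the same dose level". For AST/ALT with liver metastases, Grade 2 or below is enough.
- **Section 4.1.4, Treatment Period.** The first dose requires that the general screening requirements are still met. Before [225Ac]-FPI-2068, events related to [111In]-FPI-2107 or FPI-2053 "should be resolved to Grade 1 or baseline", with a 28-day delay accepted if resolution takes longer. Laboratory results "within retreatment criteria requirements must be documented within 48 hours prior to each cycle of" [225Ac]-FPI-2068.
- **Table 24, Cycle 2 onward.** The row is headed "Retreatment criteria (see" Table 15), but its footnote c says "Obtain within 48 hours prior to the injection and confirm that all tests are within the eligibility requirements". Footnote e says that events related to [225Ac]-FPI-2068 "should be resolved to < Grade 1 or to baseline prior to" the next administration.
- **Tables 21 to 23.** Tables 21 and 22 attach the footnote c sentence to an eligibility row that points to Sections 5.1 and 5.2. Table 23 attaches it to a combined eligibility/retreatment row that cites Table 15. For events related to [111In]-FPI-2107, Table 21 footnote d says they "should be resolved to < Grade 1 or to baseline within 14-days post" imaging dose. Tables 22 and 23 give the same grade without a day limit.

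**The concern.** These passages decide whether a participant may be dosed on a given day, and read literally they do not give one answer. Section 8 makes adherence to the schedule of activities essential and excludes waivers, so a site cannot treat the footnotes as optional. Section 6.7.3 is equally part of the protocol.

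The consequence falls mainly on Cycles 2 and 3. If one site follows the footnotes and another follows Table 15, participants at the same dose level with the same results could receive different numbers of cycles. Cumulative activity, discontinuation rates and late toxicity by dose level would then partly reflect which page was followed. Section 4.1 bases the RP2D on all available safety, efficacy, PK and dosimetry information, so this carries into the study's main output. Low-grade cytopenia is a foreseeable case: bone marrow suppression is the first risk listed in Table 5.

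**Working it through.** No power or sample-size figure is involved. The check compares the passages and then applies both sets of limits to laboratory values.

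**1. Grade to which events must resolve**

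| Event related to | Schedule footnote | Other passage |
|---|---|---|
| [225Ac]-FPI-2068, before Cycle 2 onward | Below Grade 1, or baseline (Table 24, e) | Grade 1 or baseline; Grade 2 or below for AST/ALT with liver metastases (Table 15) |
| [111In]-FPI-2107, before Cycle 1 | Below Grade 1, or baseline (Tables 21–23, d) | Grade 1 or baseline (Section 4.1.4) |

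The two columns differ for every related Grade 1 event in a participant with no such finding at baseline.

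**2. Laboratory limits, if footnote c means the entry criteria**

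Entry limits are from inclusion criterion 10. Hold limits are the mildest band listed in Table 15, with a normal baseline where Table 15 depends on baseline.

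| Test | Entry limit | Table 15 hold | Values on which they disagree |
|---|---|---|---|
| Platelets (× 10^9/L) | ≥ 100 | < 75 | 75 to < 100: entry fails, no hold |
| AST/ALT, no liver metastases (× ULN) | ≤ 3 | > 5 | > 3 to 5: entry fails, no hold |
| Bilirubin, no Gilbert's disease (× ULN) | ≤ 1.5 | > 3 | > 1.5 to 3: entry fails, no hold |
| Haemoglobin (g/dL) | ≥ 9.0 | ≤ 9 | Exactly 9.0: entry met, hold |
| ANC (× 10^9/L) | ≥ 1.5 | < 1.5 | None |
| Creatinine clearance (mL/min/1.73 m²) | ≥ 60 | 30–59 and lower bands | None |

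With a normal baseline the limits also agree for AST/ALT with liver metastases (5 × ULN) and for bilirubin in Gilbert's disease (3 × ULN). Table 15 also holds for WBC below 3 × 10^9/L, for which there is no entry limit.

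**3. One participant through both rules**

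Take a normal platelet baseline, a fall to 60 × 10^9/L before Cycle 2, and recovery to 80. These values are illustrative, and 80 is assumed to be below the local normal range. Table 15 assigns Grade 2 to values between 50 and 75, so 60 triggers a hold and 80 is Grade 1.

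- Table 15: retreat at the same dose level.
- Footnote e: 80 is neither below Grade 1 nor baseline, so the condition is not met.
- Footnote c read as the entry criteria: 80 < 100, so the condition is not met.
- Footnote c read as Table 15: 80 ≥ 75, so the condition is met.

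Footnote e and Table 15 therefore disagree whichever way footnote c is read.

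**4. Cycle 1**

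The sentence in Section 4.1.4 covering every cycle brings the retreatment criteria into Cycle 1. The same section and Tables 21 and 22 apply the screening criteria there. For platelets, AST/ALT and bilirubin the entry limits are the stricter ones, so a participant who meets them triggers no Table 15 hold on those tests. Applying both sets literally adds only haemoglobin of exactly 9.0 g/dL and WBC below 3 × 10^9/L.

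**The case against.** Much can be said in the protocol's defence.

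- **Footnote c may simply mean Table 15.** Its row in Table 24 names the retreatment criteria, and Section 6.7.3 itself speaks of being eligible for repeat dosing. This is a natural reading, and it would remove the laboratory conflict for Cycle 2 onward. Nothing in the text fixes it, however, and the identical sentence in Tables 21 and 22 refers to the entry criteria.
- **The grade wording may be a slip** for at most Grade 1, the form used in exclusion criterion 9a. That is possible, but it is printed in all four tables. The footnotes say should, which softens them without settling which grade applies.
- **The 14 and 28 days need not conflict.** Section 4.1.4 accepts the longer delay when an event needs more time, which reads as an exception to the 14-day default. This stands; only a cross-reference is lacking.
- **A hold does not automatically end treatment.** Section 6.7.3 lets the Investigator, Sponsor and Medical Monitor agree adjustments, and Section 7.1 makes a 28-day delay a reason to discontinue only without approval. This also stands. It does not supply one rule for all sites.

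A reader might go further and infer that the conflict changes who feeds the DLT decisions in Table 16. The documents do not support that. DLTs are counted in the first cycle only (Section 6.7.7), no passage waives the screening requirements before that cycle, and step 4 shows how little the extra sentence adds.

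**Conclusion.** The re-dosing conditions are wrong as written. The resolution grade contradicts Table 15 before Cycle 2 onward, and Section 4.1.4 before Cycle 1, on the plain words of each passage. The laboratory conflict is conditional: it arises only if footnote c of Tables 23 and 24 means the entry criteria. It is then limited to the four ranges in step 2, three of them under the stated baseline and disease conditions, and is not a mismatch in every test. The Cycle 1 sentence in Section 4.1.4 is loose, with little practical reach.

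The effect is mainly on who receives Cycles 2 and 3. Its size cannot be calculated, because the protocol does not say how often participants would fall in these ranges. Differences between sites are inferred from the conflicting text. Discontinuation follows only from a hold that stays unresolved without an agreed adjustment. The point still deserves correction before sites rely on it: in a first-in-human study, the same participant can be both permitted and not permitted a further dose.

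**What to change.** Reconcile the passages in an amendment:

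1. State one resolution grade for each type of event, identical in Section 4.1.4, Table 15 and the footnotes of Tables 21 to 24, including any separate provision for AST/ALT with liver metastases.
2. Make footnote c of Tables 23 and 24 name the criteria that govern Cycle 2 onward, by table or section number.
3. Limit or clarify the sentence in Section 4.1.4 that applies the retreatment criteria before every cycle, so that the Cycle 1 rule is unambiguous.
4. If the 28-day allowance in Section 4.1.4 is meant as the exception to the 14 days in Table 21 footnote d, say so there.

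The sponsor and the Safety Review Committee decide which grades and limits apply; this review takes no position on them. The cost is wording in an amendment, with no new assessment or visit.
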